6.10. Posttreatment Assessments

Upon discharge from inpatient hospitalization, the following assessments will be required at the Day 29 and Day 60 phone follow-up (see [Appendix 3](#)):

- Assessment of need for RRT
- Record the 8-point ordinal scale (see Section 6.9)
- Review AEs and document concomitant medications

- Mortality
- IMV (yes/no if yes, provide date when mechanical ventilation was started)
- Hospital readmission rate

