Appendix 3. Study Procedures Table

	Screening	Baseline/ Day 1	Day 2	Day 3	Day 4	Day 5	Day 6	Day 7	Day 8	Day 9, 10, 11	Day 12	Day 13	Day 14	Day 15	Day 16	Day 17, 18, 19	Day 20	Day 21	Day 22, 23	Day 24	Day 25, 26, 27, 28	Day 29*	Day 29 and Day 60 Phone Follow-up Visits (+ 5 days)
Written Informed Consent	X																						
Inclusion/Exclusion Criteria	X																						
Focused Medical History, including SCr values ^a	X																						
Documentation of SARS-CoV-2 Infection ^b	X																						
Complete Physical Examination	X																						
Height	X																						
Weight	X																						
Vital Signs ^c	X	X	X	X	X	X	X	X	X	X	X	X	X	X	X	X	X	X	X	X	X	X	X
Respiratory Status ^d	X	X	X	X	X	X	X	X	X	X	X	X	X	X	X	X	X	X	X	X	X	X	X
Invasive Mechanical Ventilation ^g	X	X	X	X	X	X	X	X	X	X	X	X	X	X	X	X	X	X	X	X	X	X	X
Pulmonary Radiographic Imaging ^e	X																						
8-Point Ordinal Scale ^f	X	X	X	X	X	X	X	X	X	X	X	X	X	X	X	X	X	X	X	X	X	X	X
Pregnancy Test ^h	X																						
Chemistry ^{h,r}	X	X		X		X			X		X				X		X			X		X	
Hematology ^{h,r}	X	X		X		X			X		X				X		X			X		X	

	Screening	Baseline/ Day 1	Day 2	Day 3	Day 4	Day 5	Day 6	Day 7	Day 8	Day 9, 10, 11	Day 12	Day 13	Day 14	Day 15	Day 16	Day 17, 18, 19	Day 20	Day 21	Day 22, 23	Day 24	Day 25, 26, 27, 28	Day 29*	Day 29 and Day 60 Phone Follow-up Visits (+ 5 days)	
Coagulation ^{1,f}	X	X		X		X			X		X				X		X			X		X		
Serum Creatinine ^{r,s}	X	X	X	X	X	X	X	X	X	X	X	X	X	X	X	X	X	X	X	X	X	X	X	
Urinalysis ^l	X																							
RRT Assessment ^k	X	X	X	X	X	X	X	X	X	X	X	X	X	X	X	X	X	X	X	X	X	X	X	X
Virologic Testing ^l		X		X		X		X					X					X				X		

[figure not shown]
CCI

CCI

CCI

Investigational Drug Dosing		X	X	X	X	X																		
Adverse Events	X	X	X	X	X	X	X	X	X	X	X	X	X	X	X	X	X	X	X	X	X	X	X	X
Concomitant Medications	X	X	X	X	X	X	X	X	X	X	X	X	X	X	X	X	X	X	X	X	X	X	X	X
Mortality																							X	
Hospital Readmission Rate																							X	

* All assessments to be completed through Day 29, or until discharge, whichever is earlier. If participant is discharged prior to Day 29, a phone follow-up is to be completed at Day 29 and Day 60.

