6. EFFICACY ANALYSES

6.1. Primary Efficacy Endpoint

6.1.1. Definition of the Primary Efficacy Endpoint

The primary endpoint is the composite of all-cause mortality or IMV from date of first dose through Day 29.

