- if n_{1h} or $n_{2h} = 1$, the corresponding n_{1h} or n_{2h} will be adjusted to 2, then corresponding denominator $[(n_{1h} - 1)$ or $(n_{2h} - 1)]$ is 1;
- if n_{1h} or $n_{2h} = 0$, then the corresponding stratum will be ignored, will not be included in the calculation, thus the proportion difference and 95% CI are still calculable.

15) Kidney disease status definition

Kidney disease data at baseline are collected in this study, including: history of CKD and ongoing AKI from the Medical History CRF form, ESKD status at Screening from the ENROLLMENT CRF form, and renal transplant history from the Transplant History CRF form.

Expected data patterns are as follows (renal transplant history can be present or absent for any of these combinations):

	Ongoing AKI (from MH CRF question)	History of CKD (from MH CRF question)	ESKD status at Screening (from ENROLLMENT CRF)	Kidney Disease Status
1	Yes	Any	No	AKI
2	No	Yes	No	CKD
3	Any	Any	Yes	ESKD

Kidney disease status is defined as:

- AKI: the 1st row of the above table, ie, ongoing AKI with or without history of CKD
- CKD: the 2nd row of the above table, ie, history of CKD without ongoing AKI
- ESKD: the 3rd row of the above table.

16) For demographics tables, “Not Permitted” will be excluded from percentage for detailed race categories summary (ie, race categories collected on eCRF). For combined Race Category (e.g. Asian, White, Black, Other), “Not Permitted” is included in “Other” and “Other” will be included in the count of percentage.

17) For calculation of peak serum creatinine (SCr) through Day 29 (among those without ESKD at baseline), (1) baseline records will not be included; (2) Day 1 postdose is included in the calculation; (3) for multiple records within one day, the observed record with max SCr will be selected; (4) For multiple days has the same highest value, the earliest will be picked.

18) Death date imputation

For a partial death date where the year and month are available but the date is missing, the following imputation will be performed:

- If the latest clinical date (ie, the latest of study drug start dates and end dates, the in-person or phone visit dates, the vital sign and the laboratory collection dates, including the Day 60 phone follow-up visit date) falls into the same year/month of death, then this latest clinical date will be used to impute the date of death;

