- If the latest clinical date falls into the same year, but a prior month of death, then the 1st of the month of death will be the imputed date of death;
- If the latest clinical date falls into a prior year of death, then the 1st of the month of death will be the imputed date of death.

19) The precision in reporting numerical values should be as follows:

Raw measurements will be reported the same as the data captured electronically or on the eCRF.

Standard deviation and standard error will be reported to one more significant decimal place than the raw measurement.

Mean, median, minimum, Q1, Q3, maximum, 95% CIs will be reported to the same number of decimal places of the raw measurements.

If records for the same lab use different decimal places, the decimal place with majority records would be used.

Exceptions may be considered.

20) Graded Laboratory Abnormalities Summary

The following labels will be used for laboratory abnormalities and Grade 3 or 4 laboratory abnormalities summary tables and listings:

Battery	Lab Test Label Used in l-labtox Listing	Toxicity Direction	Lab Test Label Used in t-labtox Table
Hematology	Hemoglobin	Decrease	Hemoglobin (Decreased)
	Lymphocytes	Decrease	Lymphocytes (Decreased)
	Neutrophils	Decrease	Neutrophils (Decreased)
	Platelets	Decrease	Platelets (Decreased)
	WBC	Decrease	WBC (Decreased)
Chemistry	Albumin	Decrease	Albumin (Decreased)
	Alkaline Phosphatase	Increase	Alkaline Phosphatase (Increased)
	ALT	Increase	ALT (Increased)
	AST	Increase	AST (Increased)
	Bicarbonate	Decrease	Bicarbonate (Decreased)
	Corrected Calcium	Increase	Corrected Calcium (Hypercalcemia)
	Corrected Calcium	Decrease	Corrected Calcium (Hypocalcemia)
	Creatine Kinase (CK)	Increase	Creatine Kinase (Increased)
	Creatinine	Increase	Creatinine (Increased)
	Lipase	Increase	Lipase (Increased)
	Magnesium	Decrease	Magnesium (Hypomagnesemia)
	Phosphate	Decrease	Phosphate (Hypophosphatemia)
	Serum Glucose	Increase	Serum Glucose (Hyperglycemia)
	Serum Glucose	Decrease	Serum Glucose (Hypoglycemia)
	Serum Potassium	Increase	Serum Potassium (Hyperkalemia)
	Serum Potassium	Decrease	Serum Potassium (Hypokalemia)
	Serum Sodium	Increase	Serum Sodium (Hypernatremia)
	Serum Sodium	Decrease	Serum Sodium (Hyponatremia)
	Total Bilirubin	Increase	Total Bilirubin (Hyperbilirubinemia)
Uric Acid	Increase	Uric Acid (Hyperuricemia)	
Coagulation	Prothrombin Intl. Normalized Ratio (INR)	Increase	Prothrombin Intl. Normalized Ratio (Increased)

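### SAP Appendix 2 item 18 lets the contact that reported a death anchor its imputed date, so a day-missing death by Day 29 can be dated after Day 29 or get no date

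*SAP*

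**What the plan says.** Item 18 (Death date imputation) in SAP Appendix 2 applies when year and month of death are known and the day is missing. It has three branches:

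- Same month: if the latest clinical date "falls into the same year/month of death, then this latest clinical date will be used to impute the date of death".
- Earlier month: "If the latest clinical date falls into the same year, but a prior month of death", the 1st of the month of death is used.
- Earlier year: "If the latest clinical date falls into a prior year of death", the 1st of the month of death is used.

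The latest clinical date is the latest of the dosing dates, "the in-person or phone visit dates, the vital sign and the laboratory collection dates, including the Day 60 phone follow-up visit date". Contacts made after the death are not excluded.

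Protocol 6.10 lists mortality among the post-discharge items: "Upon discharge from inpatient hospitalization, the following assessments will be required at the Day 29 and Day 60 phone follow-up". Protocol Appendix 3 gives those calls a window of +5 days.

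SAP 6.1.1 sets the window: "The primary endpoint is the composite of all-cause mortality or IMV from date of first dose through Day 29". The key α-controlled secondary endpoint, all-cause mortality (SAP 6.2), has the same Day 29 limit. SAP 3.6.1 says that missing data are generally not imputed unless a method is specified. SAP 3.8.1 makes the death date the Last Study Date for anyone who dies on study.

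**The concern.** To place a death whose day is unknown, one needs the last date on which the participant was known to be alive. Item 18 uses the last date on which anything was recorded. For a death learned by phone after discharge, that record can be the call that reported the death, which comes after the event it is meant to date.

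Two failures follow. If the call is in the month of death, the death is dated to the call, the latest date it could have. If the call is in a later month, no branch applies and the death has no date. The censoring rule in SAP 6.1.3 does not rescue this case: it refers to the last study day, and for on-study deaths SAP 3.8.1 sets Last Study Date to the death date, which is the missing value.

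At stake are Day 29 mortality, the primary composite when no IMV by Day 29 is dated, the ordinal score of 8 from the day of death, and RRT-free days. Enrolment stopped before 50% of plan (SAP 2.2 and 2.4), so each event carries more weight than planned.

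**Working it through.** **Inputs.** The three branches and the definition of the latest clinical date (SAP Appendix 2, item 18); call windows of Day 29 to 34 and Day 60 to 65 (Protocol Appendix 3); study day = date − first dose date + 1 (SAP 3.8.1); endpoint limit Day 29 (SAP 6.1.1 and 6.2). Assumption: the reporting call is recorded as a phone visit and is the latest clinical date.

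**Two worked cases.**

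| | First dose | True death | Call | Item 18 result |
|---|---|---|---|---|
| A | 1 Oct 2021 | 20 Oct (Day 20) | 31 Oct (Day 31) | Same month: dated 31 Oct, Day 31, outside the window |
| B | 10 Sep 2021 | 24 Sep (Day 15) | 10 Oct (Day 31) | Call in a later month: no branch, undated |

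In case B, 30 September is Day 21. Month and year alone prove that the death is inside the window.

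**Enumeration.** The documents give no distribution of dates, so uniform weights are assumed. Grid 1 is every first-dose date from 1 March to 31 December 2021 (306 dates) with true death on Day 6 to 29 (24 days): 306 × 24 = 7,344 combinations. Grid 2 is all of 2021 with true death on Day 2 to 29: 365 × 28 = 10,220. Both ranges are choices made for this check. Each combination is crossed with each call day.

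| Call day | Grid | Dated after Day 29 | Undated | Dated Day 29 |
|---|---|---|---|---|
| 30–34 | 1 | 19,320/36,720 = 52.6% | 17,400/36,720 = 47.4% | 0 |
| 30–34 | 2 | 23,423/51,100 = 45.8% | 27,677/51,100 = 54.2% | 0 |
| 29–34 | 1 | 43.8% | 45.8% | 10.4% |
| 29–34 | 2 | 38.2% | 52.5% | 9.3% |
| 60–65 | 1 and 2 | 0% | 100% | 0% |

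The Day 60 row follows without enumeration. Day 29 and Day 60 are 31 days apart, and two dates in one calendar month are at most 30 days apart.

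**Deaths certain to count.** In grid 1 the month of death ends by Day 29 in 3,000 of 7,344 combinations (40.8%). Any call on Day 30 to 34 is then in a later month, so these are all undated: 3,000 × 5 = 15,000 of the 17,400 undated results (86%).

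**Effect on power.** The documents do not say how many deaths are affected, so this only shows scale. The plan's 85% reproduces: RDV event rate 1 − 0.65^0.70 = 0.2603; events 372 × 0.35 + 744 × 0.2603 = 323.9; power Φ(|ln 0.70| × √(323.9 × 2/9) − 1.96) = Φ(1.066) = 85.7%. Losing 1%, 2%, 5% or 10% of events equally in both arms gives 85.3%, 85.0%, 83.9% or 81.9%.

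**The case against.** **Intent.** The three branches are complete only if the latest clinical date precedes death, which suggests that a last-alive anchor was intended. Nor do the documents say that a call answered by a relative is entered as the participant's visit date. Both are fair, and they make this a wording fault with an obvious repair. But the text excludes no post-death contact, and a programmer will implement the text.

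**Other sources of the date.** A reader might infer that post-discharge deaths are learned only at the two calls. They are not. Death is an SAE (Protocol 7.1.2), SAEs are reported throughout the study within 24 hours of the investigator's knowledge (7.3.3 and 7.4.1.1), readmitted participants have daily ordinal scores through Day 29 (6.4), and the SAP reconciles SAEs with the safety database (7.1.4). This stands: most death dates should be complete.

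**True uncertainty.** When a call after Day 29 is in the month of death, that month runs past Day 29, so a death between Day 30 and the call is possible. The enumeration removes that doubt by fixing the true death at Day 29 or earlier. This stands for the same-month failure. It does not apply to undated deaths whose month had already ended by Day 29.

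**Day 60.** A reader might infer that the Day 60 call routinely displaces deaths. An in-window Day 60 call never dates a death by Day 29 to after Day 29; it leaves the death undated. That case also needs a missed Day 29 call, since anyone found alive at that call had not died before it.

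**Conclusion.** The defect is real and narrow. Read as written, item 18 gives a wrong date or no date for a day-missing death by Day 29 when the contact that reported it falls after Day 29 and is the latest clinical date. The undated branch is the clearer fault, because it includes deaths that month and year alone place inside the window.

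The shares of about 53% and 47% are conditional on such a case with a Day 30 to 34 call, and they rest on uniform dates; the wider grid gives 46% and 54%. They are not shares of all deaths. The number of affected deaths is not given and is probably small, and the direction of any bias between arms is unknown.

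Two stronger readings are not supported. One is that every such death is lost from the primary endpoint: a participant with dated IMV by Day 29 still counts in the composite, and only the mortality endpoint is exposed. The other is that the SAP excludes undated deaths or treats them as event-free: it says neither. It leaves them without an event time, so an ad hoc decision would be needed. The CMH sensitivity analysis in SAP 6.1.4 gives no clear protection, since it counts a missing IMV/death status as no event.

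**What to change.** Amend SAP Appendix 2 item 18 before unblinding:

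1. Define the anchor as the last date known alive. Exclude the contact at which the death was reported and any later contact.
2. Give every case a date within a stated range. The lower limit is the last date known alive, or the 1st of the month of death if later. The upper limit is the report date or the end of the month of death, whichever is earlier.
3. Count the death as an event by Day 29 whenever the whole range ends on or before Day 29.
4. Where the range straddles Day 29, state one convention and repeat the primary and mortality analyses with the earliest and the latest possible dates.

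The cost is a few lines of text, one derived variable and one pair of sensitivity analyses. No new data should be needed if contact and report dates are already on the eCRF, which was not available to check.

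There is one downside. An early-date convention can pull later deaths into the window. As an illustration, take a missed Day 29 call, last known alive on Day 6 to 28, true death on Day 30 to 60, first dose March to December 2021 and uniform weights. Imputing the day after last known alive, or the 1st of the month of death when last known alive falls in an earlier month, places 104,190 of 218,178 combinations (48%) inside the window. The two-way analysis in step 4 would show this.

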6.9. Ordinal Scale

The ordinal scale is an assessment of the clinical status of a given study day. Each day, the worst (ie, highest ordinal) score from the previous day will be recorded (ie, on Day 3, the highest ordinal score from Day 2 is obtained and recorded for Day 2). The ordinal scale needs to be completed twice on Day 1: prior to randomization (for baseline predose score) and the worst score on Day 1.

The scale is as follows:

- 8) Death
- 7) Hospitalized, on IMV or ECMO
- 6) Hospitalized, on noninvasive ventilation or high-flow oxygen devices
- 5) Hospitalized, supplemental oxygen
- 4) Hospitalized, not requiring supplemental oxygen – requiring ongoing medical care for COVID-19–specific medical care (other than per-protocol RDV administration)
- 3) Hospitalized, not requiring supplemental oxygen – no longer requires ongoing medical care (other than per-protocol RDV/saline as placebo administration)
- 2) Not hospitalized, limitation on activities and/or requiring home oxygen
- 1) Not hospitalized, no limitations on activities

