6.1.3. Primary Analysis of the Primary Efficacy Endpoint

The primary endpoint will be analyzed using a stratified log-rank test stratified by the randomization strata. P value and the proportion of all-cause mortality or IMV at Day 29 from Kaplan-Meier estimate will be provided.

The hazard ratio and 95% confidence interval (CI) will be estimated using a Cox model with stratification factors as covariates.

Participants with missing outcomes for the primary endpoint due to premature discontinuation of the study on or prior to Day 29 will be censored at the last study day.

Additionally, the difference in proportions of all-cause mortality or IMV at Day 29 between treatment groups and the 95% CI for the difference will be provided based on the stratum-adjusted Mantel-Haenszel (MH) proportion as described in {Koch 1989} in [Appendix 2](#).

The FAS will be the primary analysis set for efficacy endpoint evaluation.

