6.2.1. Analysis of Secondary Efficacy Endpoints

The key α -controlled secondary endpoint of all-cause mortality through Day 29 will be analyzed in a similar manner to the primary endpoint.

Initiation of IMV through Day 29 and time to recovery through Day 29 will also be analyzed in a similar manner to the primary endpoint except that a competing risk analysis approach will be used with death as the competing risk.

For analysis on time to recovery through Day 29, two sets of analyses will be conducted:

(1) Time to recovery through Day 29, in which the first recovery without further worsening in the ordinal scale score (ie, a score of > 4) by Day 29 will be considered an event; (2) Time to recovery through Day 29, in which the first recovery (regardless of further worsening or not) will be considered an event.

The clinical status assessed by the 8-point ordinal scale at Day 15 and Day 29 will be analyzed using a proportional odds model including treatment as the independent variable. Two models will be explored; one with baseline score as a continuous covariate and one without baseline score as a covariate. The odds ratio and 95% CI will be provided. The percentage of participants in each category will be summarized by treatment group. The assumption of odds proportionality will be assessed using a score test and reported. Clinical status by study day and change from baseline up to Day 29 will also be summarized by treatment group.

For participants without ESKD at baseline, the number of RRT-free days will be calculated between date of first dose and Day 29. The number of RRT-free days will be calculated as the number of full days from Day 1 to Day 29 that the participant was alive and did not receive RRT. The number of RRT-free days will be summarized by treatment group, and compared between treatment groups using Wilcoxon rank sum test.

The proportion of participants with recovery through Day 29 will be summarized by treatment group, and compared between treatment groups using the CMH test stratified by randomization strata. Similar for time to recovery analysis, two sets of analyses will be conducted: (1) The proportion of participants with recovery through Day 29, in which recoveries without further worsening by Day 29 is considered; (2) The proportion of participants with recovery through Day 29, in which recoveries regardless of worsening status by Day 29 is considered.

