10. SOFTWARE

SAS® Software Version 9.4. SAS Institute Inc., Cary, NC, USA.

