	Prothrombin Time (PT)	Increase	Prothrombin Time (Increased)
	Activated partial thromboplastin time (aPTT)	Increase	Activated partial thromboplastin time (Increased)

21) SAS codes for the treatment comparison for demographics and baseline characteristics tables.

CMH test for nominal variable (Y), the p-value from the general association test should be used for nominal variables:

```
proc freq;  
tables trt * Y /cmh; /*general association test*/  
run;
```

CMH test for ordinal variable (Y), the p-value from the row mean score test should be used for ordinal variables:

```
proc freq;  
tables trt * Y / cmh2 ; /*row mean score test*/  
run;
```

Wilcoxon rank sum test for continuous variable (Y), the p-value from the normal approximation two-sided test should be used for continuous variables:

```
proc npar1way wilcoxon;  
class trt;  
var Y;  
run;
```

22) Proportional Odds

A proportional odds model including treatment as the independent variable and baseline score as a continuous covariate to compare the treatment groups:

```
proc logistic;  
class trt/ param=ref order=data;  
model outcome(descending)= trt baseline;  
run;
```

A proportional odds model including treatment as the independent variable to compare the treatment groups (without covariate):

```
proc logistic;  
class trt/ param=ref order=data;  
model outcome(descending)= trt;  
run;
```

where outcome is the ordinal scale response at Day 15 and Day 29.

23) Cox model :

a) with stratification factors as covariates

```
proc phreg;  
class trt strat1 strat2 strat3;  
model aval*cnsr(1) = trt strat1 strat2 strat3 /risklimits = wald;  
ods output ParameterEstimates=Est1 ModelANOVA = pvout1;  
run;
```

b) with no stratification factors as covariates

```
proc phreg;  
class trt;  
model aval*cnsr(1) = trt /risklimits = wald;  
ods output ParameterEstimates=Est1 ModelANOVA = pvout1;  
run;
```

24) log-rank test

Log-rank test between treatment groups:

```
proc lifetest;  
time aval*cnsr(1);  
strata trt;  
run;
```

The binary indicator variable (cnsr) with a value of 0 indicates the time to the event of interest is complete or 1 indicates the time to the event is censored.

25) Stratified log-rank test

Log-rank test between treatment groups:

```
proc lifetest;  
time aval*cnsr(1);  
strata strat1 strat2 strat3/group=trt;  
run;
```

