The binary indicator variable (cnsr) with a value of 0 indicates the time to the event of interest is complete or 1 indicates the time to the event is censored.

26) Competing risk analysis

The following SAS code will be used to generate the cause-specific hazard ratio and 95% confidence intervals for the competing risk analysis:

```
proc phreg;
  class trt strat1 strat2 strat3;
  model aval* cnsr (1, 2) = trt strat1 strat2 strat3 / rl;
  hazardratio "Cause-specific hazard" trt;
run;
```

where $cnsr = 0$ if the participant had the event; $cnsr = 2$ if the participant died prior to having the event, and $cnsr = 1$ if the participant did not have the event and did not die.

SAS codes to obtain a cumulative incidence function plot and dataset for further processing for time to first event table:

```
proc lifetest outcif=outcif plots=cif;
  strata trt;
  time aval* cnsr (1) / failcode = 0; *Note: this produces data for the event of interest only;
run;
```

SAS code to obtain support tables:

```
proc univariate;
  by trt cnsr;
  var aval;
  output pctlpre=P_ min=min max=max pctlpts= 10, 25, 50, 75, 90;
run;
```

27) SAS code for stratified 2-sided Wilcoxon Rank sum test (stratified on baseline result)

```
proc freq;
  table base*trt*aval/cmh2 scores=modriddit;
run;
```

where BASE is the baseline value.

28) SAS code for ANCOVA:

```
ods output ParameterEstimates=out1 LSMeans=out2 LSMeansCL=out3
LSMeansDiffCL=out4;
```

```
proc glm data=dat1 plots=none;
  class trt;
  model DAVG = trt base / solution;
  lsmeans trt / stderr cl pdiff;
run;
ods output close; quit;
```

29) SAS code for CMH test and estimates with stratification factors adjustment:

```
proc freq data=dat1;  
  tables strat1*strat2*strat3*trt*Y/ list cmh;  
ods output cmh=cmhpval CommonRelRisks=risk;  
run;
```

30) Renal and hepatic adverse events include preferred terms from search term list 'Acute Renal Failure (SMQ)' and search term list 'Acute and non-infectious liver events' MedDRA 25.0.

31) Vital signs, and SCr collected after Day 29, PCR collected after day 44 will be assigned to "Post Day 29".

CCI [REDACTED]

33) For coagulation laboratory tests, both local and Covance lab records are collected in the data. In a visit where both Covance and local lab records are collected, Covance records will be picked over local lab records.

34) Reference ranges are based on Covance laboratory reference ranges.

35) COVID-19 medications include the following drugs:

Drug name
Chloroquine

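### The SAP's Cox code names no tie method, so the default applied to whole-day times would pull the time-to-recovery hazard ratio slightly toward 1

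*SAP*

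**What the plan says.** SAP 6.1.3 separates test from estimate. On the test: "The primary endpoint will be analyzed using a stratified log-rank test stratified by the randomization strata". On the estimate: "The hazard ratio and 95% confidence interval (CI) will be estimated using a Cox model with stratification factors as covariates". SAP 6.2.1 carries this to mortality: "The key α -controlled secondary endpoint of all-cause mortality through Day 29 will be analyzed in a similar manner to the primary endpoint". It does the same for two other secondary endpoints, with death as a competing risk: "Initiation of IMV through Day 29 and time to recovery through Day 29 will also be analyzed in a similar manner to the primary endpoint".

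SAP Appendix 2 turns this into SAS code:
- Item 23a, the Cox model for the primary endpoint and mortality: "model aval*cnsr(1) = trt strat1 strat2 strat3 /risklimits = wald". Item 23b is the same without the stratification factors.
- Item 26, the cause-specific hazard ratio for IMV and recovery: "model aval* cnsr (1, 2) = trt strat1 strat2 strat3 / rl".

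None of the three MODEL statements sets a tie method, and neither the SAP nor the protocol mentions ties elsewhere. The software in SAP Section 10 is "SAS® Software Version 9.4. SAS Institute Inc., Cary, NC, USA".

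Times are whole days. SAP 3.8.1 derives study day as a difference of dates plus 1. Protocol 6.4 collects IMV start as a date. Recovery comes from the ordinal scale, of which protocol 6.9 says: "The ordinal scale is an assessment of the clinical status of a given study day". SAP 6.2.1 also sets the score to 2 on the date of discharge alive.

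**The concern.** Follow-up to Day 29 allows at most 29 distinct event times, so ties are certain. When `TIES=` is absent, PROC PHREG uses the Breslow approximation. That is a property of the software; the SAP does not say it.

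On a tied day Breslow keeps everyone who has the event that day in the denominator for every one of that day's events. Those people come disproportionately from the arm with the higher hazard, so the estimate is pulled toward 1. Efron, available in the same procedure, corrects for this. The pull grows with the share of the risk set that has the event on one day. Time to recovery is therefore the endpoint most likely to show it, if recovery is the most frequent or most front-loaded event. At stake is a small, avoidable and systematic bias in the reported recovery hazard ratio and its confidence interval.

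**Working it through.** **Inputs from the documents.** 2:1 allocation, 744 and 372 planned; placebo rate 35% and hazard ratio 0.70 for the primary endpoint (SAP 1.3). Enrollment stopped before 50% of plan (SAP 2.2), so N is at most 557. Times are in whole days to Day 29.

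**Assumed, because the documents give nothing.** 70–80% recovered by Day 29 on placebo, true recovery hazard ratio 1.30, timing from even (Weibull shape 1) to strongly front-loaded (shape 0.5). The only hint on timing is in protocol 1.4: about a third of participants with moderate COVID-19 in another trial were discharged before finishing five days of treatment.

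**The plan's own figure.** Remdesivir rate = 1 − 0.65^0.70 = 26.0%. Events = 744 × 0.260 + 372 × 0.35 ≈ 324. Power = Φ(√(324 × 2/9) × |ln 0.70| − 1.96) = 85.7%, against the stated value of about 85%. It reproduces, and it does not depend on how the Cox model treats ties.

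**Step 1: hand check with even timing.** With a constant hazard h per day and times grouped to days, Breslow in a two-arm comparison converges to the ratio of daily event probabilities, (1 − e^(−HR·h)) / (1 − e^(−h)), not to HR.
- Recovery, 70%: h = −ln(0.30)/29 = 0.04152; ratio = 0.05254/0.04067 = 1.292. On the log scale, 1 − ln 1.292/ln 1.30 = 2.4%.
- Recovery, 80%: h = 0.05550; ratio = 0.06961/0.05399 = 1.289, or 3.1%.
- Primary, 35%, HR 0.70: h = 0.01485; ratio = 0.010344/0.014745 = 0.7016, or 0.6%.

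The attenuation is about half the daily share of the risk set with an event.

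**Step 2: large-sample limits, both methods, varied timing.**

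| Scenario | Breslow, even to shape 0.5 | Efron | Breslow loss of log HR |
|---|---|---|---|
| Recovery 70%, HR 1.30 | 1.292 to 1.281 | 1.299–1.300 | 2.4% to 5.6% |
| Recovery 80%, HR 1.30 | 1.289 to 1.273 | 1.299–1.300 | 3.1% to 8.0% |
| Primary 35%, HR 0.70 | 0.7016 to 0.7031 | 0.7000 | 0.6% to 1.2% |
| Rarer event 20%, HR 0.70 | 0.7008 to 0.7015 | 0.7000 | 0.3% to 0.6% |

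With a true HR of 1, both methods return 1.

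**Step 3: simulated trials, N = 557.**
- With the three stratification covariates and death censoring recovery (75% recovering, 40% by Day 5), the mean recovery HR was 1.287 with Breslow and 1.302 with Efron. The shift was 0.11 of the standard error of 0.107.
- In the same run the primary log HR moved by 0.003 (0.02 SE) and the IMV log HR, at an assumed 15% placebo rate, by 0.001 (under 0.01 SE).
- With recoveries bunched around Days 5–7 (82% recovering, SE 0.101 for both methods), Breslow gave 1.281 and Efron 1.296. Against Efron the shift is ln(1.296/1.281)/0.101 = 0.12 SE. Against the truth it is ln(1.30/1.281)/0.101 = 0.15 SE.
- The 8% extreme from Step 2, set against the same SE, is ln(1.30/1.2731)/0.101 ≈ 0.21 SE.

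**The case against.** The strongest reply is that this hardly matters, and most of that reply stands.

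- **No confirmatory decision moves.** Only the primary endpoint and mortality are alpha-controlled (SAP 3.5), and both are tested by stratified log-rank.
- **The shift is small against the uncertainty.** A shift of 0.15 SE lowers nominal 95% coverage to about 94.8%. At N = 250 the simulated recovery shift was only 0.08 SE.
- **The recovery figures rest on assumed rates and timing.**

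A reader might also infer more than the documents support:

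- *Every hazard ratio is materially distorted.* For the primary endpoint, mortality and IMV the shift is about 0.001–0.003, mostly invisible at two decimals. The pull is a tendency, not a certainty in each dataset: at N = 250 Breslow was nearer 1 in 77% (IMV), 88% (primary) and 96% (recovery) of simulated trials.
- *The trial loses power for recovery.* In the bunched scenario, power from the Cox z statistic was 71.0% with Breslow and 74.5% with Efron, but that describes Cox Wald inference. SAP 6.2.1 refers recovery to the manner of the primary analysis, whose test is the log-rank.
- *The Cox hazard ratio is the only effect measure.* Item 26 also produces cumulative incidence by arm, and SAP 6.2.1 compares the proportion recovered with a stratified CMH test under two definitions.

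What the reply does not remove is that the code, run as written, uses the less accurate of two readily available methods on the endpoint where the difference is likely to be largest. The bias is systematic and does not shrink with sample size.

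**Conclusion.** The point holds as a minor one. Run as written, items 23a, 23b and 26 apply Breslow to day-level times. Under the stated assumptions the recovery log hazard ratio comes out about 3–5% too close to 0, and up to about 8% with strong front-loading. The documents can confirm neither the size nor that recovery is the most affected endpoint. The direction follows from the grouping of times and holds whenever the true hazard ratio differs from 1. Only the Cox hazard ratios and their confidence intervals change; the planned log-rank and CMH tests, the proportions and the cumulative incidence estimates stay as they are.

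**What to change.** Add `TIES=EFRON` to the MODEL statements in SAP Appendix 2 items 23a, 23b and 26, and add one sentence to SAP 6.1.3 and 6.2.1 saying that ties in the Cox models are handled by the Efron method. The cost is one keyword in three lines of code and two sentences; no new data are needed. If the SAP is already final, SAP Section 1 requires later changes to be documented in the clinical study report, and the Breslow result for time to recovery should be shown beside the Efron result there. Low priority.
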